### **Study Design**

This was an experimental, randomized study with a control session. The sample consisted of 21 women practicing pole dance at an intermediate level. Each participant performed two sessions on different days: one experimental session, which consisted of a 60-minute pole dance class, and one control session, which consisted of 60 minutes of seated rest without physical effort. The order of the sessions was defined randomly to ensure balance and minimize bias.

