### **Procedures**

At the beginning of the study, participants underwent an anamnesis to collect sociodemographic data, lifestyle information, comorbidities, and details related to pole dance practice. Anthropometric measurements, including weight, height, and body mass index, were also recorded. In the experimental session, participants completed a 60-minute pole dance class, which included a 15-minute warm-up with joint mobility and stretching exercises, followed by 10 minutes of strength and resistance training combined with transitions. The next 15 minutes focused on aerial movements using the static pole, while another 15 minutes were dedicated to sequences on the spinning pole. The session concluded with a 5-minute passive stretching period. In the control session, participants remained seated for 60 minutes without performing any physical effort.

Blood pressure and heart rate were measured using a digital sphygmomanometer (Omron HEM-7113) at five time points: before the session, immediately after, and at 15, 30, and 45 minutes post-session. Participants were instructed to avoid caffeine, alcohol, smoking, and vigorous physical activity in the 24 hours prior to data collection. Perceived exertion was assessed at the end of the experimental session using the Borg modified scale (0–10).

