### **Statistical Analysis Plan**

Data analysis was performed using SPSS version 17.0. Descriptive statistics were used to characterize the sample, with continuous variables expressed as mean and standard deviation, and categorical variables expressed as absolute and relative frequencies. Differences in systolic blood pressure, diastolic blood pressure, and heart rate between sessions and across time points were analyzed using repeated measures ANOVA (session  $\times$  time), followed by Bonferroni post-hoc tests. Spearman's correlation coefficient was applied to examine associations between blood pressure, heart rate, and perceived exertion. A significance level of  $p < 0.05$  was adopted for all analyses.

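### The pre-session reading is one of five ANOVA time levels, no baseline adjustment is planned, and no term is named for the 45-minute SBP hypothesis: a loss of efficiency, not a bias

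*Combined protocol and SAP*

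**What the plan says.** Study Design describes a two-session crossover. "The sample consisted of 21 women practicing pole dance at an intermediate level", and "Each participant performed two sessions on different days". On allocation, "The order of the sessions was defined randomly to ensure balance and minimize bias"; the split between the two orders is not given.

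Procedures has blood pressure and heart rate taken "at five time points: before the session, immediately after, and at 15, 30, and 45 minutes post-session".

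The Statistical Analysis Plan analyses differences in the three outcomes "between sessions and across time points were analyzed using repeated measures ANOVA", with session and time as factors, "followed by Bonferroni post-hoc tests". The contrasts in that post-hoc family are not listed. A 0.05 level "was adopted for all analyses". No covariate appears, and no time level is set aside as baseline. The fair reading is a time factor with five levels, one before the session and four after, although the plan does not say so outright.

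Expected Results points to an SBP reduction at 45 minutes after the pole dance session, but the analysis section does not tie that expectation to a main effect, the interaction or a particular post-hoc test. No SD, correlation, effect size or sample-size calculation is given.

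**The concern.** Each woman has her own pre-session reading on both days. A reading that the session cannot have affected can be handled as an outcome level, as a reference to subtract, or as a covariate, and the choice affects precision.

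- As an outcome level, it is averaged into the session main effect and pulls that effect towards zero.
- As the reference in the session × time contrast, it is subtracted in full, noise included.
- As a covariate, it is subtracted only to the extent that it predicts the post-session value.

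With 21 women and single-day blood pressure readings, the difference can matter for the one hypothesis the study states. Leaving the deciding term unnamed also means that tests with very different power could each be taken as the answer.

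**Working it through.** **Inputs.** From the documents: 21 women, both sessions each, five time points, level 0.05 (two-sided assumed). Everything else below is an assumption. There is no planned figure to reproduce.

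**Set-up.** Work with each woman's difference, pole dance minus control, at each time. Stable differences between women cancel. Take the variance of this difference as 1 at every time, and let r be the correlation between the pre-session and 45-minute differences.

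**1. Session main effect.** With no pre-session difference and a constant effect of −0.60 SD afterwards, the five-level average is (0 + 4 × (−0.60))/5 = −0.48, a loss of one fifth. In simulation (4,000 runs, n = 21, r = 0.5, equal correlation between all times), power was 0.91 with the four post-session levels and 0.76 with all five.

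**2. Interaction.** The contrast (45 minutes minus pre), compared between sessions, estimates the full −0.60, so there is no dilution. At r = 0.5 the 4-df interaction test had power 0.77 for the constant effect. For a rise then fall (+0.6, 0, −0.3, −0.6) it had power above 0.99. For that profile the main effect averages −0.3/5 = −0.06 and had power 0.06, or 0.07 without the pre-session level.

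**3. Precision at 45 minutes.** Relative variances are:

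- post-only comparison: 1
- change from pre-session: 2(1−r)
- adjusted for the pre-session difference: 1−r²

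The saving over change is 1 − (1−r²)/[2(1−r)] = (1−r)/2. The saving over post-only is r².

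| r | Change | Adjusted | Saving over change | Saving over post-only |
|---|---|---|---|---|
| 0.2 | 1.60 | 0.96 | 40% | 4% |
| 0.5 | 1.00 | 0.75 | 25% | 25% |
| 0.8 | 0.40 | 0.36 | 10% | 64% |
| 0.9 | 0.20 | 0.19 | 5% | 81% |

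**4. Small-sample check.** These savings are asymptotic. The approximate difference detectable with 80% power is s/√21 × (t₀.₉₇₅ + t₀.₈₀), on 20 df unadjusted. For the adjusted contrast it uses 19 df and a variance inflated by 1 + 1/18 for the estimated slope. In SD units:

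| r | Change | Post-only | Adjusted |
|---|---|---|---|
| 0.2 | 0.813 | 0.643 | 0.649 |
| 0.5 | 0.643 | 0.643 | 0.574 |
| 0.8 | 0.407 | 0.643 | 0.397 |
| 0.9 | 0.287 | 0.643 | 0.289 |

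So the gain over change is gone by r = 0.9, and the gain over post-only is absent at r = 0.2. An order term takes one further df.

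**5. Power at 45 minutes** for 0.6 SD, change / post-only / adjusted: 0.54 / 0.73 / 0.72 at r = 0.2; 0.74 / 0.74 / 0.83 at r = 0.5; 0.99 / 0.75 / 0.99 at r = 0.8.

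**6. In mmHg.** Assume session SD 4, residual SD 5 and a 5 mmHg fall, so r = 16/(16 + 25) = 0.39. Simulated power was about 0.59 for change, 0.66 to 0.67 for post-only and 0.71 to 0.72 adjusted.

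**7. Validity.** With no effect, rejection rates in the simulations lay between 0.04 and 0.06 for every method.

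**The case against.** The planned model contains a session × time interaction, and that is the term best placed to detect a 45-minute fall. It is not diluted, and for a rise-then-fall profile removing the pre-session level rescues almost nothing in the main effect. A post-only comparison at 45 minutes is also a natural post-hoc test under the plan, and against it the gain in the mmHg scenario is about 5 points of power rather than 12. The crossover has already removed stable differences between women, so a gain typical of a parallel-group trial cannot be borrowed. All of this stands, and it limits the point.

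Three stronger readings are tempting, and the documents do not support them.

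- **That the ANOVA dilutes the session effect as such.** Only the main effect is attenuated, and the one-fifth figure holds only if the effect is constant after the session.
- **That the change contrast overstates the fall through regression to the mean.** Session order is randomised, so a chance high baseline is as likely on either day, and the contrast is unbiased overall. Conditionally there is something in it. In the mmHg scenario with no true effect, in the roughly 7% of trials where the pole dance baseline was more than 3 mmHg higher, the change score showed a mean fall of 2.3 mmHg, against 0.1 after adjustment.
- **That adjustment is worth a fixed number of extra women.** At r = 0.4 the asymptotic ratio 1.20/0.84 = 1.43 suggests 30 women in place of 21. The simulated standard errors of 2.19 and 1.88 mmHg give (1.88/2.19)² = 0.74, or about 28 (21/0.74). Either figure depends on an assumed r and on comparison with the change score alone.

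What the objection does not remove is that the deciding contrast is unnamed and that a covariate already measured goes unused.

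**Conclusion.** The point holds as one of efficiency and specification; the planned tests are not invalid. The plan does not name the term that tests the 45-minute SBP hypothesis, and the candidates differ widely in power. If the main effect is used, a constant effect is attenuated by one fifth. If the contrast with pre-session is used, it carries more variance than the adjusted contrast by a factor of 2/(1+r): 1.67 at r = 0.2, 1.33 at 0.5 and 1.11 at 0.8. With 21 women the advantage vanishes near 0.9. Against a post-only comparison the gain is negligible at r = 0.2 and large at high r. The direction is secure under equal variance of the session difference across times. The size is not known, because the documents give neither r nor any SD. The change is worth making but is not essential to validity.

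**What to change.** Name one primary contrast: the pole-dance-minus-control SBP difference at 45 minutes. Regress it on the pole-dance-minus-control pre-session SBP difference, left uncentred, and on session order coded −1/+1. The intercept is then the effect at equal baselines, averaged over the two orders. Do the same for DBP and heart rate.

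The order coding must be written down. With 0/1 coding the intercept is the effect in one order only. In the mmHg scenario with an 11/10 split, power fell to 0.42, and with a 3 mmHg shift by order the estimate was −8.0 for a true −5.0.

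For all times jointly, fit a linear mixed model to the post-session readings, with own-day and participant-mean baseline as covariates so that slopes within and between women are not mixed. Keep changes from pre-session within each session as descriptive or secondary results, since the expected return of heart rate to baseline is described in those terms.

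Cost: no new data, and 2 df in the primary regression. That regression still needs both pre-session and both 45-minute readings from each woman, so it does not by itself retain women with a missing one. Timeline says the analyses have been finalised, so the result should be reported openly as a revised or sensitivity analysis, beside the planned ANOVA, and not presented as prespecified.

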**NCT number: [to be filled after registration]**

**Document date:22/07/2022**

## **Study Protocol and Statistical Analysis Plan**

### **Introduction**

Pole dance (PD) combines aerobic and isometric components, with potential to influence cardiovascular variables. The primary objective of this study was to evaluate the acute blood pressure response after a single PD session in young normotensive women. The hypothesis was that a PD session would promote post-exercise hypotension for systolic blood pressure (SBP), without significant changes in diastolic blood pressure (DBP).

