### **Expected Results**

It was expected that systolic blood pressure would show a significant reduction 45 minutes after the experimental session, while diastolic blood pressure would remain unchanged. Heart rate was anticipated to increase immediately after the pole dance session, followed by a gradual return to baseline values during the recovery period.

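### The plan specifies no within-woman difference or confidence interval, so a non-significant result in 21 women cannot show that diastolic pressure is unchanged or rule out a relevant systolic fall

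*Combined protocol and SAP*

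**What the plan says.** The Introduction sets the aim: "The primary objective of this study was to evaluate the acute blood pressure response after a single PD session in young normotensive women". The hypothesis that follows is a systolic fall, "without significant changes in diastolic blood pressure (DBP"). Expected Results repeats this in the same terms: "systolic blood pressure would show a significant reduction 45 minutes after the experimental session", with diastolic pressure staying as it was.

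The design is paired. Study Design states: "The sample consisted of 21 women practicing pole dance at an intermediate level", and "Each participant performed two sessions on different days", in random order. Under Procedures, readings are taken "at five time points: before the session, immediately after, and at 15, 30, and 45 minutes post-session".

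The Statistical Analysis Plan says that differences "between sessions and across time points were analyzed using repeated measures ANOVA", with a session-by-time structure, Bonferroni post-hoc tests and a 0.05 significance level throughout. Means and SDs are planned, but as a description of the sample. Spearman coefficients are planned for associations with perceived exertion. No section names a between-session mean difference, the SD of such a difference, an effect size or a confidence interval. No section gives a smallest relevant change, an expected SD, a power calculation or a basis for 21 women.

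**The concern.** Part of the hypothesis is a claim of no effect. A plan that reports only whether p falls below 0.05 lets a non-significant diastolic result stand as evidence for that claim, when it may only reflect a small sample. The same trap exists for systolic pressure: a non-significant result is easily written up as no hypotension while a relevant fall remains compatible with the data.

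The planned means and SDs do not close the gap. Each woman is her own control, so precision depends on the SD of the within-woman difference. SDs by session and time include the spread between women and do not give that quantity. A reader of the planned output could not tell which sizes of response the trial has ruled out.

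**Working it through.** The plan states no power, effect size or SD, so there is no figure of its own to reproduce.

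**Inputs from the documents.** n = 21, two sessions per woman, a pre-session reading and four post-session readings, significance level 0.05.

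**Assumptions, because the documents are silent.**
- Tests are two-sided.
- The within-woman SD of a single reading, s, is 4 to 7 mmHg, and the four readings in the contrast have independent errors.
- The Bonferroni family has 1, 4 or 10 comparisons.

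**Step 1: interval width.** The control-adjusted change is (post − pre) in the pole dance session minus (post − pre) in the control session. It uses four readings, so its variance is 4s² and its SD is 2s. With 20 degrees of freedom, t(0.975) = 2.086, and

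half-width = 2.086 × SD / √21 = 0.455 × SD.

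| s (mmHg) | SD of paired difference, 2s | SE = 2s/√21 | 95% half-width |
|---|---|---|---|
| 4 | 8 | 1.7 | 3.6 |
| 5 | 10 | 2.2 | 4.6 |
| 7 | 14 | 3.1 | 6.4 |

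If the interval is Bonferroni-adjusted, the multiplier rises from 0.455 to 0.60 (4 comparisons) or 0.69 (10 comparisons). At SD 10 that is about 6.0 or 6.9 mmHg.

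**Step 2: how often a real change is missed.** From the noncentral t distribution, for one unadjusted 5% test:

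| SD of paired difference | True change 3 mmHg missed | True change 5 mmHg missed |
|---|---|---|
| 5 | 26% | 1% |
| 8 | 63% | 22% |
| 10 | 74% | 41% |
| 12 | 81% | 56% |

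Power of 80% needs a true effect of 0.64 SD unadjusted, 0.79 SD with 4 comparisons and 0.88 SD with 10. Over much of this range a non-significant result says little about the absence of an effect.

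**Step 3: exaggeration among significant results.** An estimate must reach about 0.455 SD to be significant. By simulation (400,000 draws per setting, unadjusted 5% test):

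| True effect (SD units) | Power | Mean significant estimate ÷ truth |
|---|---|---|
| 0.3 | 26% | 1.87 |
| 0.4 | 42% | 1.49 |
| 0.5 | 59% | 1.28 |
| 0.6 | 74% | 1.15 |
| 0.8 | 94% | 1.03 |
| 1.0 | 99% | 1.00 |

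Exaggeration is therefore material only below about 0.6 SD. In mmHg that is 0.6 × 8 = 4.8 to 0.6 × 14 = 8.4, depending on s. With Bonferroni over 4 to 10 comparisons the boundary moves up to about 0.8 to 0.9 SD.

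**Step 4: why SDs by session and time are no substitute.** Suppose the between-woman SD is 10 and s = 5 (both assumed). The SD at one session and time is √(100 + 25) = 11.2. An SE for the control-adjusted change rebuilt from such SDs, ignoring the pairing, is 2 × 11.2/√21 = 4.9 mmHg. The paired value is 2.2 mmHg.

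**The case against.** Several points on the other side are fair.

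- *The objective does not ask for size.* It asks for the response to be evaluated, and a directional hypothesis follows. A reader might infer that the analysis contradicts an estimation objective; the text does not go that far. The gap remains, because the hypothesis contains a no-change claim that a test alone cannot support.
- *The plan is not limited to p-values.* Means, SDs and Spearman coefficients are planned, and an output that is not named is not necessarily withheld. This stands: it is a gap in specified reporting, and the data can still answer the question. But none of the planned summaries gives the precision of the paired difference.
- *A reported fall is likely to be exaggerated.* This is the tempting stronger reading, and the documents do not support it, because they give neither an SD nor an effect. Over reading SDs of 4 to 7 mmHg and true falls of 3 to 8 mmHg, the factor runs from about 1.0 to 2.5. Exaggeration also comes from selecting on significance at low power. An interval displays the imprecision but leaves a significant point estimate as it is; what helps is reporting every time point whatever its p-value.
- *The contrast above may not be the one the post-hoc tests use.* True: the plan does not say. A simple paired comparison of two readings has SE √2 × 5/√21 = 1.54 mmHg at s = 5, and a half-width of 2.086 × 1.54 = 3.2 mmHg. Power for 3 and 4 mmHg is then 46% and 69% before Bonferroni, which pushes the other way. The simple comparison is narrower, but it drops either the control session or the pre-session reading.
- *No section says that a non-significant systolic result would mean no hypotension.* Correct. The direct textual support concerns diastolic pressure; the systolic point is a risk of interpretation.

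**Conclusion.** The point holds as a gap in the analysis plan that should be corrected. As written, non-significance in 21 women could stand as proof that diastolic pressure did not change, and no planned output would show how large a change the data leave open. On the assumed reading SDs, a result centred on zero would still be compatible with changes of about 3.6 to 6.4 mmHg in either direction, and more if the interval is Bonferroni-adjusted.

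The factor of 0.455 depends only on the 21 women and a two-sided 95% interval. The mmHg figures rest on the assumed SDs and on independent reading errors. The finding does not extend to saying that a significant systolic fall would probably be overstated; that is conditional on a true effect below about 0.6 SD of the paired difference. Nor does it mean that the trial is unable to estimate its effect.

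**What to change.** Add to the Statistical Analysis Plan:

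> For SBP, DBP and heart rate, the mean within-woman difference (pole dance minus control) in change from the pre-session reading is reported at every post-session time point, regardless of significance, with the SD of that paired difference and its 95% confidence interval. The conclusion on SBP is drawn from the 45-minute interval. DBP is described as unchanged only to the extent that its interval excludes relevant changes, and not because p exceeds 0.05.

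Naming 45 minutes for SBP follows the time already singled out in Expected Results. Leave Expected Results as it stands: it is a recorded prior expectation and should not be rewritten after the study. The Timeline says the study was completed in 2023, so the added text should be marked as made after data collection. The same applies to any margin for a relevant DBP change, since the documents give none.

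The cost is one paragraph and one results table from data already held. The downside is that the intervals will look wide, about ±4 to ±6 mmHg on the assumptions above.

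### The single-step Bonferroni post-hoc tests are valid but needlessly conservative; Holm's step-down method costs nothing in error control and mainly helps the late heart-rate comparisons

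*Combined protocol and SAP*

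**What the plan says.** The Statistical Analysis Plan section analyses "Differences in systolic blood pressure, diastolic blood pressure, and heart rate between sessions and across time points" by repeated measures ANOVA, "followed by Bonferroni post-hoc tests", at a 0.05 significance level throughout. It names no step-down version and does not say which comparisons make up the Bonferroni family.

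Four other statements bear on the point:

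- Study Design: "The sample consisted of 21 women practicing pole dance at an intermediate level", and "Each participant performed two sessions on different days". Comparisons are therefore paired, with 20 degrees of freedom.
- Procedures: readings were taken "at five time points: before the session, immediately after, and at 15, 30, and 45 minutes post-session".
- Expected Results, heart rate: "Heart rate was anticipated to increase immediately after the pole dance session, followed by a gradual return to baseline values".
- Expected Results, SBP: "systolic blood pressure would show a significant reduction 45 minutes after the experimental session". No immediate rise in SBP is mentioned.

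The document gives no effect size, SD, within-person correlation, power figure or sample-size calculation.

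**The concern.** Bonferroni tests every comparison at 0.05/m, where m is the number of comparisons in the family. It keeps that threshold even when several comparisons are certain to be rejected. Holm uses the same threshold for the smallest p-value and relaxes it after each rejection. The difference is largest when a family mixes very large effects with small ones.

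The plan expects that mixture for heart rate: a rise right after the class, then smaller differences as it settles. The late, small differences show how far recovery has gone by 45 minutes, and they bear the cost of the unchanged threshold. With only 21 women, a true residual elevation could more easily be missed. The same could apply to the later SBP readings, but only if something else in the SBP family is also rejected.

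**Working it through.** **1. Inputs from the documents.** n = 21, paired, 20 df; five time points; alpha 0.05, taken as two-sided because sidedness is not stated. Five times give 5 × 4 / 2 = 10 pairwise comparisons within a session, 4 comparisons with baseline, or 5 class-versus-control comparisons. There is no stated power figure to reproduce.

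**2. Thresholds.** Bonferroni: 0.05/10 = 0.005, or 0.05/4 = 0.0125, for every test. Holm: the i-th smallest p-value is compared with 0.05/(m − i + 1), stopping at the first failure. For m = 4 the thresholds are 0.0125, 0.0167, 0.025 and 0.05.

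**3. Why Holm never loses.** Any p-value at or below 0.05/m passes every Holm step, so all Bonferroni rejections are kept. If m0 nulls are true, at least m0 hypotheses remain when the first false rejection occurs, so that p-value is at most 0.05/m0. By the union bound this has probability at most m0 × 0.05/m0 = 0.05, whatever the dependence. The chance of at least one rejection is the same under both methods, because the first step is the same.

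**4. A direct check on one case.** Assume a residual +5 bpm at 45 minutes and an SD of paired differences of 8. The noncentrality is 5 × √21 / 8 = 2.86. Noncentral-t power is 41% at 0.005, 56% at 0.0125 and 78% at 0.05. In the four-comparison family, if the three earlier times are rejected first, Holm tests the 45-minute difference at 0.05 where Bonferroni uses 0.0125.

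**5. Simulation.** Paired t tests, n = 21, independent errors scaled to the stated SD of paired differences, with both methods applied to the same p-values. Repeat runs agree within about two points. All means (bpm or mmHg) and SDs are assumptions. Mean changes at 0, 15, 30 and 45 minutes:

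- Heart rate: +30, +14, +9, +5
- SBP with an immediate rise: +10, 0, −3, −5
- SBP without it: 0, 0, −3, −5
- SBP with a 45-minute fall only: 0, 0, 0, −5

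| Comparison | Family | SD | Bonferroni | Holm | Gain (points) |
|---|---|---|---|---|---|
| Heart rate, 45 min | 10 pairs | 8 | 41% | 69% | 28 |
| Heart rate, 45 min | 10 pairs | 10 | 23% | 43% | 20 |
| Heart rate, 45 min | 4 vs baseline | 8 | 56% | 78% | 22 |
| Heart rate, 45 min | 4 vs baseline | 10 | 35% | 59% | 24 |
| SBP with rise, 30 min | 10 pairs | 6 | 23% | 36% | 13 |
| SBP with rise, 45 min | 10 pairs | 6 | 74% | 83% | 9 |
| SBP with rise, 45 min | 10 pairs | 8 | 41% | 51% | 10 |
| SBP with rise, 30 min | 5 class vs control | 8 | 16% | 20% | 4 |
| SBP with rise, 45 min | 5 class vs control | 8 | 52% | 57% | 5 |
| SBP without rise, 30 min | 10 pairs | 6 | 23% | 28% | 5 |
| SBP without rise, 30 min | 10 pairs | 8 | 10.7% | 12.4% | 1.7 |
| SBP without rise, 30 min | 4 vs baseline | 8 | 18.2% | 20.7% | 2.5 |
| SBP, 45-min fall only | 10 pairs | 8 | 41.8% | 44.3% | 2.5 |
| SBP, 45-min fall only | 4 vs baseline | 8 | 56.4% | 56.4% | 0.0 |
| SBP, 45-min fall only | 5 class vs control | 8 | 52.4% | 52.5% | 0.1 |

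**6. A second set of assumptions.** Effects in SD units, within-person correlation 0.5 to 0.7 (results given in that order).

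- Heart rate (+2.0, +0.8, +0.5, +0.4) at 45 minutes: m = 4, 21.2% → 35.4% to 38.0% → 57.9%; m = 10, 12.5% → 20.2% to 24.9% → 38.8%. The smallest gain is 20.2 − 12.5 = 7.7 points.
- SBP −0.5 at 45 minutes with a +1.0 immediate rise: m = 4, 35.5% → 40.0% to 58.2% → 63.3%; m = 10, 23.1% → 31.1% to 45.0% → 56.4%.
- SBP −0.5 at 45 minutes as the only change: m = 4, 35.1% → 35.2% to 60.2% → 60.3%; m = 10, 23.1% → 24.3% to 44.4% → 47.2%.
- Holm's family-wise error was at most 4.8% in every scenario of this set.

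**The case against.** The strongest defence is that nothing here is invalid. Bonferroni controls family-wise error for any set of comparisons and has matching simultaneous intervals, which Holm lacks in simple form. With 21 women, an interval around the SBP change may tell a reader more than an extra significance flag. This stands: the point is about efficiency. It does not justify keeping Bonferroni p-values, because intervals can be shown beside Holm p-values and the plan does not call for simultaneous intervals.

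A reader might infer that Bonferroni seriously weakens the test of the SBP hypothesis. The documents do not support that. The larger SBP gains need a clear immediate rise in SBP, and neither the Introduction nor Expected Results states one; only heart rate is expected to rise. The largest gains therefore fall on heart rate, while the primary objective concerns blood pressure.

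A reader might also infer that Bonferroni tilts the study towards confirming heart-rate recovery. Expected Results says heart rate rises, "followed by a gradual return to baseline values during the recovery period"; it does not say recovery is complete by 45 minutes. Reading a non-significant difference as recovery would be a separate error, which Holm does not cure.

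Finally, the undefined family matters about as much as the method. With a 45-minute SBP fall of 5 and SD 8, Bonferroni power is 42% for ten comparisons and 56% for four, a wider gap than Holm gives for SBP. Changing the method without naming the family would leave that open.

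**Conclusion.** The point holds as an efficiency improvement. That Holm rejects at least as much at the same 5% family-wise error needs no assumption. The size of the gain does, because the documents give no effects, SDs, correlations or family.

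- **Heart rate at 45 minutes:** about 8 to 28 points of power for a true residual elevation, given a large immediate rise.
- **SBP with a clear immediate rise:** about 5 to 13 points at 30 to 45 minutes in most scenarios, and 4 to 5 for the class-versus-control family at SD 8.
- **SBP without that rise:** about 0 to 3 points at 45 minutes and up to about 5 at 30 minutes.

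The ANOVA session-by-time test is unaffected.

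**What to change.** In the Statistical Analysis Plan, replace "followed by Bonferroni post-hoc tests" with wording such as: *followed by Holm step-down adjusted paired comparisons, family-wise alpha 0.05 within each outcome, the family being [the four post-session times versus baseline within the class session / the class-versus-control comparisons at each time].* One family should be chosen and stated. Show unadjusted or Bonferroni intervals beside the Holm p-values, labelled as such.

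The arithmetic is small: order the unadjusted paired p-values and compare them in turn with 0.05/m, 0.05/(m − 1), and so on. The real cost is in reporting. The Timeline section describes the study as completed in 2023 and its analyses as finalized, so moving now to a method that can only reject more is a post hoc change. Disclose it, and report the Holm results beside the planned Bonferroni results rather than in their place.
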